11.2.7. Severe TEAEs

Severe TEAEs will be summarized by SOC and PT.

A subject data listing of all severe AEs (both TEAEs and non-TEAEs) will be listed.

11.2.8. TEAEs Leading to Drug Withdrawal

All TEAEs leading to drug withdrawal will be summarized by SOC and PT as well as by PT only (in descending order of subject incidence).

A subject data listing of TEAEs leading to drug withdrawal will be provided.

11.2.9. TEAEs Leading to Drug Interruption

All TEAEs leading to drug interruption will be summarized by SOC and PT.

11.2.10. TEAEs of Special (Specific) Interests

The diarrhea characterization CRF collects information at each visit: what event occurred, if the event meets protocol definition (yes or no), and frequency of watery/liquid stools (Daily, 5 – 6 days per week, 2 – 4 days per week, Once every other week to once a week, Once a month or less). Protocol-defined diarrhea refers to diarrhea adverse events that have two or more watery or liquid stools in a day.

Summarization will include:

- Subject incidence of protocol-defined diarrhea TEAE;
- Total number of diarrhea event and protocol-defined diarrhea TEAE;
- Protocol-defined diarrhea TEAE characteristics of highest frequency of watery/liquid stools, duration and onset day of the event,

The summaries will be provided for the placebo-controlled period, and for the apremilast-exposure period.

A listing for diarrhea events will be provided.

11.2.11. TEAEs and Serious TEAEs by Subgroups

All TEAEs and serious TEAEs will be summarized by sex (male, female), age category (< 65 , ≥ 65 years), race (White, non-White), and region (Japan, other; Europe, North America, Asia, and Rest of the World), provided sufficient subjects are enrolled into these categories.

11.2.12. TEAEs Leading to Drug Withdrawal by Subgroups

All TEAEs leading to drug withdrawal will be summarized by sex (male, female), age category (< 65 , ≥ 65 years), race (White, non-White), and region (Japan, other; Europe, North America, Asia, and Rest of the World)), provided sufficient subjects are enrolled into these categories.

11.2.13. Deaths

All TEAEs leading to death will be summarized by SOC and PT. A subject data listing of deaths will be provided.

All TEAEs occurring after the date of the last dose of IP and up to 28 days after the last dose of IP will also be summarized by SOC and PT for subjects who enter the Observational Follow-up Phase. The EAIR will not be provided in this summary.

11.3. Clinical Laboratory Evaluations

Laboratory parameters as specified in protocol 6.6.7 will be included.

Laboratory marked abnormalities (see Section 16.3) will be summarized using subject incidence and EAIR for each marked abnormality based on subjects with a baseline value and at least one post-baseline value for criteria requiring baseline or subjects with at least one post-baseline value for criteria not requiring baseline. Laboratory marked abnormalities will also be summarized for subjects with normal values at baseline and for subjects with abnormal values at baseline separately. For the purposes of these summaries, subjects with abnormal (normal) values at baseline are defined as those whose baseline value is low (not low) for criteria concerning low values and those whose baseline value is high (not high) for criteria concerning high values; both low and high are relative to the laboratory normal range.

Summary statistics of observed values and changes from baseline in continuous laboratory parameters will be provided by time points. Numeric values reported as less than ($<$) or greater than ($>$) a laboratory-defined limit will be included with the " $<$ " or " $>$ " signs ignored. Frequency summaries of shifts from baseline category to the category of post-baseline time points, the end of treatment and to the worst post-baseline category in terms of normal/abnormal (low or high) or grade will be provided in the above hematology and serum chemistry parameters.

A subject data listing of all laboratory data sorted by subject ID and date of sample collection will be provided based on the safety population, irrespective of analysis periods.

11.4. Vital Signs and Weight

Summary statistics of observed values and changes from baseline in vital signs (including weight, for which percent change from baseline will also be summarized) will be provided over time. Frequency summaries (shift tables) of shifts from baseline to post-baseline time points and to the worst post-baseline value in terms of normal/abnormal will be provided for pulse,

respiratory rate and blood pressure. The normal ranges are defined as: 60-100 beats/minute for pulse, 12 to 16 breaths/minutes for respiratory rate, 90-140 mmHg for systolic blood pressure, and 60-90 mmHg for diastolic blood pressure).

Vital sign abnormalities will be summarized in a manner similar to laboratory marked abnormalities. A subject data listing of vital sign abnormalities will be provided. Frequency summaries of change and percent change in weight from baseline to the end of the period will be provided by baseline BMI category (< 18.5 , ≥ 18.5 to < 25 , ≥ 25 to < 30 , ≥ 30 kg/m²) and by baseline weight category (< 50 , ≥ 50 to 60 , ≥ 60 to < 70 , ≥ 70 to < 85 , ≥ 85 kg). The categories of weight change (kg) and percent change (%) are < -20 , ≥ -20 to < -10 , ≥ -10 to < -5 , ≥ -5 to < 0 , 0 , > 0 to ≤ 5 , > 5 to ≤ 10 , > 10 to ≤ 20 , and > 20 . The end-of-period value is the last post-baseline value in the analysis period (excluding the value obtained at the follow-up visit, if applicable) up to 28 days after the last dose of IP in the study.

A subject data listing of all vital signs and weight data sorted by subject ID and date of measurement will be provided based on the safety population, irrespective of analysis periods.

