4.2.2. Safety Endpoints

Safety and tolerability as defined by the following:

- Type, frequency, severity, and relationship of the AEs to apremilast
- Number of subjects who prematurely discontinue IP due to any AE
- Frequency of clinically significant changes in vital signs, and/or laboratory findings

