16.3. Marked (Atypical) Abnormalities Criteria

Table 5: Marked Abnormalities Criteria

| Category / Analyte | SI Units | Criteria |
|-----------------------------------|--------------------|--|
| Chemistry / | | |
| Alanine Aminotransferase (SGPT) | U/L | > 3 xULN |
| Albumin | Kg/m ³ | < 25 |
| Alkaline Phosphatase | U/L | > 400 |
| Aspartate Aminotransferase (SGOT) | U/L | > 3 x ULN |
| Total Bilirubin | µmol/L | > 1.8 x ULN |
| Blood Urea Nitrogen | mmol/L | > 15 |
| Calcium | mmol/L | < 1.8 > 3.0 |
| Creatinine | µmol/L | > 1.7 x ULN |
| Glucose | mmol/L | < 2.8 > 13.9 |
| Hemoglobin A1C | % | > 9 |
| Lactate Dehydrogenase | U/L | > 3 x ULN |
| Magnesium | mmol/L | > 1.2 |
| Phosphate | mmol/L | < 0.64 > 1.60 |
| Potassium | mmol/L | < 3.0 > 5.5 |
| Sodium | mmol/L | < 130 > 150 |
| Urate | µmol/L | Male: > 590; Female: > 480 |
| Hematology / | | |
| Hemoglobin | g/L | Male: < 105, Female: < 85 Male: > 185, Female: > 170 |
| Leukocytes | 10 ⁹ /L | < 1.5 |
| Lymphocytes | 10 ⁹ /L | < 0.8 |
| Neutrophils | 10 ⁹ /L | < 1.0 |
| Platelets | 10 ⁹ /L | < 75 > 600 |
| Vital Signs / | | |
| Systolic Blood Pressure | mmHg | Increase > 10 but ≤ 15 (mild) Increase > 15 but ≤ 20 (moderate) Increase > 20 (severe) |
| Diastolic Blood Pressure | mmHg | Increase > 5 but ≤ 10 (mild) Increase > 10 but ≤ 15 (moderate) Increase > 15 (severe) |

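### Vital-sign counts in the SAP do not separate low from high, and the marked-abnormality criteria cover only rises in blood pressure, so a shift in pulse or a fall in pressure may be masked in those counts

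*SAP*

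**What the plan says.** SAP 11.4 defines the normal ranges as "60-100 beats/minute for pulse, 12 to 16 breaths/minutes for respiratory rate, 90-140 mmHg for systolic blood pressure" and "60-90 mmHg for diastolic blood pressure". Each has a lower and an upper limit. The shift tables built on them show "shifts from baseline to post-baseline time points and to the worst post-baseline value in terms of normal/abnormal". No low/high split is written, and the worst value is not defined for a measure that can be abnormal in either direction.

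SAP 11.3, the section just before, describes the laboratory shift tables as going to the "worst post-baseline category in terms of normal/abnormal (low or high) or grade". Protocol 10.7 likewise names low, normal and high for laboratory shifts. For vital signs it promises only descriptive summaries by visit.

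SAP 11.4 also says that vital-sign abnormalities are summarised in the way used for laboratory marked abnormalities. The only vital-sign criteria, in SAP 16.3 (Table 5), are graded increases: above 10 mmHg for systolic pressure and above 5 mmHg for diastolic. There is no criterion for a decrease, for pulse or for respiratory rate.

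The related safety endpoint in SAP 4.2.2 is "Frequency of clinically significant changes in vital signs, and/or laboratory findings".

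**The concern.** A treatment that moves a vital sign takes subjects out of one tail of a two-sided range and puts them into the other. If both tails are counted as abnormal, the two movements offset. The pooled count can stay flat, or even fall, while the tail of interest grows. Table 5 does not make up for this: a fall in pressure produces fewer flagged increases, and the falls themselves are not flagged.

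At stake is whether the planned categorical tables would show how many subjects per arm had low pressure or fast pulse. A safety reader would want that count, not least because diarrhea is the event of special interest (Protocol 6.6.1.1).

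**Working it through.** The plan states no figure on this point, so there is none to reproduce. Range limits and criteria come from SAP 11.4 and Table 5. The seven post-baseline visits to Week 12 are Visits 3 to 9 in Protocol Table 1. Baseline means, SDs and shifts are not in the documents; **all are assumptions**.

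**Individual cases.** Systolic 150 to 85 is abnormal to abnormal, so no shift is shown. The change of -65 meets no Table 5 criterion. Systolic 120 to 85 falls in the same shift cell as 120 to 145. The second is a rise of 25 and is flagged in Table 5; the first is not.

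**One visit.** For limits L and U, mean μ, SD σ and shift δ:

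pooled abnormal = Φ((L − μ − δ)/σ) + 1 − Φ((U − μ − δ)/σ)

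This is smallest when μ + δ equals the midpoint (L + U)/2, and grows with distance from it. The midpoints are 80 for pulse, 115 for systolic and 75 for diastolic. So the pooled count falls if the shift brings the mean nearer the midpoint, is unchanged if it ends equally far on the other side, and rises otherwise. Example (pulse mean 72, σ = 10, δ = +5): low goes from Φ(−1.2) = 11.5% to Φ(−1.7) = 4.5%; high goes from 1 − Φ(2.8) = 0.3% to 1 − Φ(2.3) = 1.1%.

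| Assumed setting | Low | High | Pooled |
|---|---|---|---|
| Pulse 72, SD 10, +5 | 11.5% → 4.5% | 0.3% → 1.1% | 11.8% → 5.5% |
| Pulse 76, SD 10, +8 | 5.5% → 0.8% | 0.8% → 5.5% | 6.3% → 6.3% |
| Pulse 80, SD 10, +5 | 2.3% → 0.6% | 2.3% → 6.7% | 4.6% → 7.3% |
| Systolic 125, SD 15, −10 | 1.0% → 4.8% | 15.9% → 4.8% | 16.8% → 9.6% |
| Systolic 120, SD 15, −10 | 2.3% → 9.1% | 9.1% → 2.3% | 11.4% → 11.4% |
| Systolic 115, SD 15, −10 | 4.8% → 15.9% | 4.8% → 1.0% | 9.6% → 16.8% |

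**Any abnormal value over seven visits, subjects normal at baseline.** By simulation: visit value = subject mean + shift + within-subject error. Between- and within-subject SDs are 8 and 6 for pulse, 11 and 8 for systolic. Repeat runs agree to about 0.2 percentage points. The tail of interest is high for pulse and low for systolic.

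| Assumed setting | Tail of interest | Pooled | Reading |
|---|---|---|---|
| Pulse 74, +6 | 2.1% → 9.4% | 22.3% → 14.9% | reversed |
| Pulse 78, +6 | 5.2% → 18.2% | 16.3% → 20.8% | visible, no direction |
| Pulse 80, +6 | 7.8% → 24.1% | 15.6% → 25.6% | visible, no direction |
| Systolic 120, −8 | 5.3% → 18.1% | 23.3% → 22.9% | cancelled |
| Systolic 118, −8 | 7.0% → 22.0% | 21.6% → 25.8% | visible, no direction |
| Systolic 120, −12 | 5.2% → 28.6% | 23.4% → 30.7% | visible, no direction |

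**Table 5 at one visit.** Take systolic SD 15 and an assumed correlation of 0.6 with baseline. The SD of change is 15 × √(2 × (1 − 0.6)) = 13.4. With no effect, P(rise > 20) = 1 − Φ(20/13.4) = 6.8%. With a fall of 10 it is 1 − Φ(30/13.4) = 1.3%. Falls of more than 20 go from 6.8% to Φ(−10/13.4) = 22.8%, and no criterion counts them.

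**The case against.** **Pooling is inferred.** SAP 11.1 describes vital-sign, weight and laboratory shifts together as normal/abnormal or grade, and 11.3 then adds low or high for the laboratory case. The short phrase may be an umbrella term, and table shells, which are not in the documents, could split it. This stands as a caution. Even so, 11.4 does not add the split that 11.3 does, and no shell layout would supply the criteria missing from Table 5.

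**Direction is available elsewhere.** This also stands. SAP 5.1 includes minimum, quartiles and maximum in the summary statistics, and 11.4 applies summary statistics to observed values and changes over time. Full listings are planned. Protocol 6.6.2 has investigators report clinically significant abnormal vital signs as adverse events, and SAP 11.2.2 tabulates these by preferred term. A reader might infer that no planned frequency table can show low pressure or fast pulse; the adverse-event tables can, where the investigator judges the finding clinically significant. A reader might also take the out-of-range count to be the safety endpoint. The endpoint refers to clinically significant changes, which is not the same thing.

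**The illustration can be chosen to suit.** Correct: small changes in the assumed mean move the result from reversal to a visible rise.

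**Fluid loss is watched in other ways.** Diarrhea has its own summaries (SAP 11.2.10), weight change is tabulated by direction (11.4), and Table 5 has criteria for urea, creatinine, sodium and potassium. The point should not be read as saying that consequences of diarrhea would go unseen.

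**Conclusion.** The point holds, within limits. On the plain reading of SAP 11.4 and Table 5, the objective categorical vital-sign counts do not distinguish low from high, and falls in pressure and changes in pulse are in no marked-abnormality summary.

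The size is conditional. Under the assumed values, a real shift is reversed (pulse mean 74, +6: about 22% to 15%), cancelled (systolic mean 120, −8: about 23% in both), or visible without direction (pulse mean 78, +6: 16% to 21%; systolic mean 118, −8: 22% to 26%). The documents give no baseline means with which to choose between these. It would be wrong to conclude that the tables will hide a signal, or that there is one to hide: the documents report no apremilast effect on pulse or pressure.

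Efficacy inference is untouched, and so is the protocol's commitment to descriptive summaries by visit. This is a gap in table specification that should be closed.

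**What to change.** In SAP 11.4:

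- Classify pulse, respiratory rate, systolic and diastolic pressure as low, normal or high against the ranges already given there.
- Replace the single shift to the worst value by two: to the lowest and to the highest post-baseline value.
- Beside the increases in Table 5, summarise decreases in pressure by counting subjects with values below the 11.4 lower limits (90 mmHg systolic, 60 mmHg diastolic).

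This needs no new data, visits or thresholds. The cost is SAP wording and an extra panel in existing tables, which become slightly longer. If the shells already split low and high, the text need only say so, and the Table 5 addition remains.

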11.5. Physical Examination

Physical examination results will not be summarized.

11.6. Electrocardiogram

A 12-lead ECG will be performed during the Screening Phase. The site will use its own, local ECG machines for the study. ECG reading will be interpreted by the investigator and recorded as: normal; abnormal, not clinically significant; or abnormal, clinically significant.

A subject data listing of all ECG data sorted by subject ID and date of measurement will be provided based on the safety population, irrespective of analysis periods.

12. INTERIM ANALYSIS

No interim analysis is planned prior to the analysis of the primary efficacy endpoint and the planned analyses are stated in Section 2.

CELGENE PROPRIETARY INFORMATION

[figure not shown]
CELGENE PROPRIETARY INFORMATION

CELGENE PROPRIETARY INFORMATION

14. CHANGES TO THE STATISTICAL SECTION OF THE PROTOCOL

No change has been made to the statistical section of the protocol.

The following additional endpoints, described in Section 4.2.1.3, will be analyzed as described in Section 10.2.4 and Section 10.3.

CELGENE PROPRIETARY INFORMATION

16. APPENDICES

16.1. Handling of Dates

Dates will be stored as numeric variables in the SAS analysis files and reported in DDMMYY format (ie, the Date9. datetime format in SAS). Dates in the clinical database are classified into the categories of procedure dates, log dates, milestone dates, outcome dates, and special dates.

- **Procedure Dates** are the dates on which given protocol-specified procedure are performed. They include the dates of laboratory testing, physical examinations, tumor scans, etc. They should be present whenever data for a protocol-specified procedure are present and should only be missing when a procedure are marked as NOT DONE in the database. Procedure dates will not be imputed.
- **Log Dates** are dates recorded in CRF data logs. Specifically, they are the start and end dates for adverse events and concomitant medications/procedures. They should not be missing unless an event or medication is marked as *ongoing* in the database. Otherwise, incomplete log dates will be imputed according to the rules in Appendix 16.2 (ie, for duration or cycle assignment, etc). However, in listings, log dates will be shown as recorded without imputation.
- **Milestone Dates** are dates of protocol milestones such as randomization, study drug start date, study drug termination date, study closure date, etc. They should not be missing if the milestone occurs for a subject. They will not be imputed.
- **Outcome Dates** are dates corresponding to study endpoints such as survival, progression, etc. In most cases they are derived either from a milestone (eg, the survival date is derived from the death date), or a procedure date (eg, the progression date is derived from the date of the tumor scan that was used to determine progression). They may be subject to endpoint-specific censoring rules if the outcome did not occur, but are not otherwise subject to imputation.
- **Special Dates** cannot be classified in any of the above categories and they include the date of birth. They may be subject to variable-specific censoring and imputation rules.

Dates recorded in comment fields will not be imputed or reported in any specific format.

16.1.1. Calculation Using Dates

Calculations using dates (ie, subject's age or relative day after the first dose of study drug) will adhere to the following conventions:

- Study days after the start day of study drug will be calculated as the difference between the date of interest and the first date of dosing of study drug (e.g., lenalidomide) plus 1 day. The generalized calculation algorithm for relative day is the following:

- If $\text{TARGET DATE} \geq \text{DSTART}$ then $\text{STUDY DAY} = (\text{TARGET DATE} - \text{DSTART}) + 1$;
- Else use $\text{STUDY DAY} = \text{TARGET DATE} - \text{DSTART}$.

Note that Study Day 1 is the first day of treatment of study drug. Negative study days are reflective of observations obtained during the baseline/screening period. Note: Partial dates for the first study drug are not imputed in general. All effort should be made to avoid incomplete study drug start dates.

- Age (expressed in days) is calculated: $\text{AGE} = \text{CONSENT} - \text{DATE of BIRTH} + 1$. In practice, age will be transformed to years by dividing the difference by 365.25 days, then truncating.
 - Preference is for using calculated age from clinical database. When not available, calculated age from CRF or IVRS may be used
 - Partial birth date: impute missing day as 15th of the month; impute missing month as July; set missing age for missing year
- Intervals that are presented in weeks will be transformed from days to weeks by using (without truncation) the following conversion formula:

$$\text{WEEKS} = \text{DAYS} / 7$$

- Intervals that are presented in months will be transformed from days to months by using (without truncation) the following conversion formula:

$$\text{MONTHS} = \text{DAYS} / 30.4167$$

16.2. Date Imputation Guideline

16.2.1. Impute Missing Adverse Events/ Prior or Concomitant Medications

Incomplete Start Date:

Missing day and month

- If the year is the **same** as the year of the first dosing date, then the day and month of the first dosing date will be assigned to the missing fields.
- If the year is **prior to** the year of first dosing date, then December 31 will be assigned to the missing fields.
- If the year is **after** the year of first dosing, then January 1 will be assigned to the missing fields.

Missing day only

- If the month and year are the **same** as the year and month of first dosing date, then the first dosing date will be assigned to the missing day.

- If either the year of the partial date is **before** the year of the first dosing date or the years of the partial date and the first dosing date are the same but the month of partial date is **before** the month of the first dosing date, then the last day of the month will be assigned to the missing day.
- If either the year of the partial date is **after** the year of the first dosing date or the years of the partial date and the first dose date are the same but the month of partial date is **after** the month of the first dosing date, then the first day of the month will be assigned to the missing day.
- If the stop date is not missing, and the imputed start date is after the stop date, the start date will be imputed by the stop date.

Missing day, month, and year

- No imputation is needed, the corresponding AE will be included as TEAE.

Incomplete Stop Date: If the imputed stop date is before the start date, then the imputed stop date will be equal to the start date.

Missing day and month

- If the year of the incomplete stop date is the **same** as the year of the last dosing date, then the day and month of the last dosing date will be assigned to the missing fields.
- If the year of the incomplete stop date is **prior to** the year of the last dosing date or prior to the year of the first dosing date, then December 31 will be assigned to the missing fields.
- If the year of the incomplete stop date is **prior to** the year of the last dosing date but is the same as the year of the first dosing date, then the first dosing date will be assigned to the missing date.
- If the year of the incomplete stop date is **after** the year of the last dosing date, then January 1 will be assigned to the missing fields.

Missing day only

- If the month and year of the incomplete stop date are the **same** as the month and year of the last dosing date, then the day of the last dosing date will be assigned to the missing day.
- If either the year of the partial date is **not equal to** the year of the last dosing date or the years of the partial date and the last dosing date are the same but the month of partial date is **not equal to** the month of the last dosing date, then the last day of the month will be assigned to the missing day.

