5.2. Analysis Periods

For the purposes of data analysis and reporting, 2 analysis periods are defined as follows, unless otherwise defined for a specific tabulation. Data analysis and reporting for a specific analysis period will include all data measured or collected (based on date of measurement or date of specimen collection, as appropriate) during that analysis period.

- Placebo-controlled period:

This period starts on the date of the first dose of IP, and stops

- on the date the first dose of apremilast is administered at the Week 12 visit (Visit 9), or
- on the date of the last study visit (including the ET Visit and the Observational Follow-up Visit; i.e., all data after the start date will be included) for efficacy analyses, or 28 days after the last dose of IP or the date of death (if applicable), whichever comes first, for safety analyses, for whom IP is not dispensed at Week 12

The start day is exclusive and the stop day is inclusive for efficacy, and safety analyses based on laboratory, vital signs, and weight. For AE analyses, the start day is inclusive, and the stop day under the first bullet is exclusive and the stop day under the second bullet is inclusive.

- Apremilast-exposure period:

This period starts

- on the date the first dose of apremilast is administered for subjects who are randomized to an apremilast dose group, or
- on the date the first dose of apremilast is administered at the Week 12 (Visit 9) for subjects who were originally randomized to placebo and switched to the APR 30 BID group,

and this period stops

- For efficacy analyses, on the date of the last study visit (including the ET visit and the Observational Follow-up Visit; i.e., all data after the start date of the apremilast-exposure period will be included), or
- For safety analysis, 28 days after the last dose of apremilast for subjects who have completed the study or have discontinued early, or the date of death (if applicable), whichever comes first.

The start day is exclusive and stop date is inclusive for efficacy analyses, and safety analyses of laboratory, vital signs, and weight. For AE analyses, both the start date and stop date are inclusive.

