11.2.3. Common TEAEs

TEAEs with subject incidence $\geq 5\%$ in any treatment group will be summarized by SOC and PT as well as by PT only in descending order of subject incidence.

Summaries about the most frequent TEAEs will include onset day of the most frequent TEAE, and the duration of those most frequent TEAE. The most frequent TEAEs will be those identified in the $\geq 5\%$ summaries noted above.

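### The partial-date rules for adverse events ignore the Week 12 switch, so some of placebo switchers' post-switch events drop out of the apremilast-exposure tables; two stop-date rules also conflict

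*SAP*

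**What the plan says.** **Start dates (SAP 16.2.1).** The only reference date is the first dosing date.

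- Day and month missing, year of first dosing: "then the day and month of the first dosing date will be assigned to the missing fields".
- Day and month missing, later year: "then January 1 will be assigned to the missing fields".
- Day missing, month of first dosing: "then the first dosing date will be assigned to the missing day".
- Day missing, later month: "then the first day of the month will be assigned to the missing day".
- Date wholly missing: "No imputation is needed, the corresponding AE will be included as TEAE". No analysis period is given.

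If the imputed start falls after a known stop date, the start is moved back to the stop date. That guard can only make a start earlier.

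**Analysis periods (SAP 5.2).** For subjects dosed at Week 12, the placebo-controlled period ends at the first apremilast dose at Visit 9, and for AEs that day is excluded. The apremilast-exposure period begins "on the date the first dose of apremilast is administered at the Week 12 (Visit 9) for subjects who were originally randomized to placebo".

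**Stop dates (SAP 16.2.1).** A year-only stop in a year before the year of last dosing is set to 31 December. A further bullet covers a stop year that is before the year of last dosing "but is the same as the year of the first dosing date, then the first dosing date will be assigned to the missing date". An imputed stop before the start is set equal to the start.

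**Outputs affected.** SAP 11.2.3: "Summaries about the most frequent TEAEs will include onset day of the most frequent TEAE, and the duration of those most frequent TEAE". SAP 11.2.10 plans onset day and duration for protocol-defined diarrhea.

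**The concern.** Period assignment depends on a date that the imputation rules never consult. A switcher's first dosing date is the first placebo dose, so a partial date compatible with both periods is resolved to the placebo side. The risk is highest just after Visit 9, when switchers are titrated on apremilast for the first time, and Protocol 8.3 explains titration as a way to mitigate GI side effects. The clause in SAP 4.2.6.1 that counts an unclear event as treatment-emergent unless data show otherwise settles treatment-emergent status, not the period.

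At stake are the completeness of the switchers' column in the apremilast-exposure tables, the onset-day and exposure-interval summaries in both arms, and the duration summaries.

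**Working it through.** The documents give no figure on this point, so the rules were applied as written.

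**Assumptions.** First dose on each of the 365 days of 2015, equally likely; first Visit 9 apremilast dose on Day 85 (first dose + 84 days); each true onset day equally likely. A post-switch event is misplaced if first dose ≤ imputed start < first dose + 84 days.

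| True onset | Date pairs | Day missing | Day and month missing |
|---|---|---|---|
| Days 85–91 | 365 × 7 = 2,555 | 87% | 99% |
| Days 85–113 | 365 × 29 = 10,585 | 51% | 96% |
| Days 85–197 | 365 × 113 = 41,245 | 13% | 84% |
| Days 85–449 | 365 × 365 = 133,225 | 4% | 50% |

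**Hand check of the 50%.** Two routes lead to it.
- Onset in the year of first dosing, imputed to Day 1: 281 + 280 + … + 1 = 281 × 282 / 2 = 39,621 pairs.
- First dose so late in the year that the switch falls after 1 January of the next year. A year-only event in that next year goes to 1 January, still before the switch. There are 83 such first-dose dates, with 365 down to 283 onset days each: 83 × (365 + 283) / 2 = 26,892 pairs.
- (39,621 + 26,892) / 133,225 = 66,513 / 133,225 = 49.9%.

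For day-missing dates, only events in the calendar month of the switch are misplaced, and none if the switch was on the 1st.

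**Worked example (assumed dates).** First placebo dose 14 March 2016, switch 6 June 2016.

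| True onset | Known | Imputed | Period |
|---|---|---|---|
| 9 June 2016 | June 2016 | 1 June 2016 | placebo-controlled (wrong) |
| 9 June 2016 | 2016 | 14 March 2016 | placebo-controlled (wrong) |
| 6 July 2016 | July 2016 | 1 July 2016 | apremilast-exposure (right) |
| 2 May 2017 | 2017 | 1 January 2017 | apremilast-exposure (right) |

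**Where a misplaced switcher event goes.** It is dated before the apremilast-exposure period, so those tables omit it at any lock. SAP Section 2 bases placebo-controlled safety on a database cut at Week 12/Visit 9 and does not say how AE records with partial dates are treated.
- Cut by visit or record date: the event appears in neither period's summaries, only in the all-AE listing of SAP 11.2.
- Cut by imputed start date: it is counted under placebo.

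**Apremilast arm.** Exposure starts at randomization, so a back-dated event stays in the exposure tables with too early an onset.

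**Stop date.** First dose 1 February 2017, dosing into 2018, AE start 10 April 2017, stop 2017.
- 31 December bullet: 10 April to 31 December inclusive = 21 + 31 + 30 + 31 + 31 + 30 + 31 + 30 + 31 = 266 days.
- First-dosing-date bullet: the stop becomes 1 February, before onset, is reset to 10 April, and the AE lasts 1 day.

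The 64 treatment weeks are 64 × 7 = 448 days, more than a year, so dosing of every Active Treatment Phase completer spans at least two calendar years and meets the condition for this clash.

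**Would a plain change of anchor do?** No. With the Visit 9 dose date in place of the first dosing date, 0% of post-switch events are misplaced, but only 82% of true placebo-phase events with the day missing, and 12% with day and month missing, stay in the placebo-controlled period.

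**The case against.** A reader might infer three stronger things that the documents do not support.

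1. *All undated events go to placebo.* They do not. A wholly missing date is not imputed. The first dosing date is often only the comparator: many events receive 1 January or the first of their own month and land in the right period.
2. *Post-Week-12 events enter the 12-week safety comparison.* This is possible, not established. The comparison uses the Visit 9 cut, and a cut by visit would exclude them.
3. *The 12-week comparison is tilted toward the drug.* The rules are the same in both arms. If late records did enter, the apremilast arm's active-phase events would be pulled back as well, offsetting the switchers' shift. Only the loss from the switchers' apremilast-exposure tables has a fixed direction.

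Other points are fair. SAP 16.1 says AE log dates should not be missing unless the event is ongoing, and that listings show dates as recorded. AEs are asked about at every visit, so year-only dates should be rare. Protocol 10.7 plans no inferential safety testing. These limit the size but leave the rule as it is.

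SAP 9.1 defines a first dose date per period, so first dosing date in 16.2.1 could be read per period. But 16.2.1 does not say so, and 16.1.1 ties Study Day 1 to the first day of study drug. That reading would also amount to the plain change of anchor tested above.

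The first-dosing-date stop bullet can be read as an exception to the 31 December bullet. The text does not say so, and for an on-treatment AE with onset after Day 1 the exception always gives 1 day. The bullet does have a use: 16.2.1 also governs medications, and without it a drug stopped before first dosing could appear to run to 31 December, through a phase in which Protocol 9.2 prohibits colchicine and topical corticosteroids.

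**Conclusion.** The point holds in limited form. Applied as written, SAP 16.2.1 dates some of placebo switchers' post-switch AEs before their first apremilast dose and so removes them from the apremilast-exposure tables. The events concerned are those with only the year known, when that year is the first-dosing year (or the next year, if the switch falls in it), and those with only the day missing in the switch month. In the apremilast arm no event is lost, but onset is wrong. The stop-date conflict is a separate fault that affects the duration summaries.

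The shares of 50% and 4% over Days 85 to 449 are proportions of partially dated post-switch events under uniform dates, not of all AEs. Real onsets concentrated after the switch would raise them. The documents do not give the number of partial dates, so no absolute bias can be stated; it is likely small. A SAP correction is still worth making, because it is cheap and the early post-switch weeks are the most exposed.

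**What to change.** In SAP 16.2.1, before the database lock:

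1. **AE start dates.** If the partial start date and any stop date are compatible with onset on or after the Visit 9 apremilast dose, and the AE was not recorded at or before Visit 9, impute the later of the current rule's date and the Visit 9 dose date. State that an AE first recorded after Visit 9 does not enter the placebo-controlled tables on an imputed date alone. Assign the period of wholly missing dates by the same test.
2. **Stop dates.** For AEs with onset on or after first dose, apply only the 31 December rule where the two bullets overlap. Keep the first-dosing-date bullet for medications, worded as an explicit exception to the 31 December bullet.

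Cost: a few lines of SAP text and programming. The start rule needs the record or visit date of each AE; the SAP shows visit-level collection only for the diarrhea form (11.2.10), so its availability for other AEs must be confirmed. A true placebo-phase event first reported after Visit 9 could move to the apremilast period, and apremilast-period counts may rise slightly.
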